# 12.0 SOURCE DOCUMENTS AND ACCESS TO SOURCE DATA / DOCUMENTS

Each participating site will maintain appropriate medical and research records for this trial, in compliance with ICH E6, Section 4.9 and regulatory and institutional requirements for the protection of confidentiality of participants. Each site will permit authorized representatives of UKZN BREC, its designees, and appropriate regulatory agencies such as SAHPRA to examine (and when required by applicable law, to copy) clinical records for the purposes of quality assurance reviews, audits, and evaluation of the study safety and progress. These representatives will be permitted access to all source data, which include, but are not limited to, hospital records, clinical and office charts, laboratory notes, memoranda, evaluation checklists, pharmacy dispensing records, recorded data from automated instruments, copies or transcriptions certified after verification as being accurate and complete, microfiches, photographic negatives, microfilm or magnetic media, x-rays, and participant files and records kept at the pharmacy, at the laboratories, and medico-technical departments involved in the clinical trial. Data collection forms will be derived from the CRFs and be provided by the UCSF study team in collaboration with the site and DF Net Data Management.

# 13.0 QUALITY CONTROL AND QUALITY ASSURANCE

The data management company DF Net Research, Inc. will implement quality control procedures beginning with the data entry system and generate data quality control checks that will be run on the database. Any missing data or data anomalies will be communicated to the site(s) for prompt clarification and resolution.

The investigational site is responsible for conducting routine quality control (QC) and quality assurance (QA) activities to internally monitor study progress and protocol compliance. A Clinical Quality Management Plan (CQMP) is in place for ensuring compliance with the protocol, applicable federal regulations, and Good Clinical Practice guidelines.

The Principal Investigator will provide direct access to the trial-related site, source data/documents, and reports for the purpose of monitoring and auditing by the sponsor, and inspection by local and regulatory authorities.

The Principal Investigator will ensure all study personnel are appropriately trained and applicable documentations are maintained on site.

# 14.0 ETHICS/PROTECTION OF HUMAN SUBJECTS

# 14.1 Ethical Standard

The investigator will ensure that this study is conducted in full conformity with the principles set forth in the Belmont Report: Ethical Principles and Guidelines for the Protection of Human Subjects of Research of the US National Commission for the Protection of Human Subjects of Biomedical and Behavioral Research (April 18, 1979) and codified in 45 CFR Part 46 and/or the ICH E6; 62 Federal Regulations 25691 (1997).

## 14.2 Institutional Review Board

Each participating institution will provide for the review and approval of this protocol and the associated informed consent documents and recruitment material by an appropriate independent ethics committee (IEC) or IRB registered with the OHRP. Any amendments to the protocol or consent materials will also be approved before they are placed into use.

# 14.3 Informed Consent Process

Informed consent is a process that is initiated prior to the participant's agreeing to participate in the study and continuing throughout the participant's study participation. Extensive discussion of risks and possible benefits of this therapy will be provided to the participant and their families.

The study coordinator will approach individual FRESH study participants about joining the parallel LACTIN-V study. The FRESH cohort has included sub-studies before (additional blood draws, high-frequency genital mucosal sampling), thus we anticipate that the overall idea will be acceptable and not stigmatizing to women enrolled in the FRESH cohort. Probiotics for gut health are relatively common over-the-counter products in South Africa. Thus, while less information is available about using 'probiotic-like' products in the vagina, we do not anticipate significant challenges with recruitment of FRESH participants into the LACTIN-V study.

The consent form describing in detail the study interventions, products, study procedures, and risks are given to the participant and written documentation of informed consent is required prior to starting intervention or administering study product. The consent form will be IRB-approved (at UKZN BREC, UCSF CHR and Ragon Institute IRB) and the participant will be asked to read and review the document. Upon reviewing the document, the investigator will explain the research study to the participant and answer any questions that may arise. The participants will sign the informed consent document available in English and isiZulu prior to any procedures being done specifically for the study. The participants should have the opportunity to discuss the study with their surrogates or think about it prior to agreeing to participate. The participants may withdraw consent at any time throughout the course of the trial. An Assessment of Understanding form, available in English and isiZulu, will be completed to ensure that study participants retained the most important aspects of the provided information.

A copy of the informed consent document will be given to the participants for their records.

The rights and welfare of the participants will be protected by emphasizing to them that the quality of their medical care will not be adversely affected if they decline to participate in this study.

# 14.4 Exclusion of Women, Minorities, and Children (Special Populations)

This trial will enrol adult women who meet the participant inclusion criteria regardless of religion or ethnic background.

The following populations will be excluded from study participation:

#### Pregnant women

Pregnant women are not eligible for this study because there are no current recommendations for the use of LACTIN-V during pregnancy.

Men

Men are not eligible for this study as the study evaluates the uterine cervix and vagina for changes associated with the use of LACTIN-V.

#### Children

Children under the age of 18 are not eligible for this study, which requires participants to be sexually experienced.

# 14.5 Subject Confidentiality

Participant confidentiality is strictly held in trust by the participating investigators, their staff, and the sponsor(s) and their agents. This confidentiality is extended to cover testing of biological samples and genetic tests in addition to the clinical information relating to participating participants.

The study protocol, documentation, data, and all other information generated will be held in strict confidence. No information concerning the study, or the data will be released to any unauthorized third party without prior written approval of the sponsor.

The study monitor or other authorized representatives of the sponsor may inspect all documents and records required to be maintained by the investigator, including but not limited to, medical records (office, clinic, or hospital) and pharmacy records for the participants in this study. The clinical study site will permit access to such records.

## 14.6 Study Discontinuation

If the trial is discontinued, participants who sign the informed consent form, and are randomized and treated will continue to be followed for safety assessments. No further study product will be administered.

# 15.0 DATA HANDLING AND RECORD KEEPING

The investigator is responsible for ensuring the accuracy, completeness, legibility, and timeliness of the data reported.

Data collection forms will be derived from the CRFs to record and maintain data for each participant enrolled in the study. All source documents should be completed in a neat, legible manner to ensure accurate interpretation of data. Permanent ink is required to ensure clarity of reproduced copies. When making a change or correction, the original entry should be crossed out with a single line, and the change should be initialed and dated. Do not erase, overwrite, or use correction fluid or tape on the original.

Data reported in the CRF should be consistent with the data collection form/source documents or the discrepancies should be documented.

The sponsor and/or its designee will provide guidance to investigators on making corrections to the data collection forms and CRFs.

# 15.1 Data Management Responsibilities

All source documents and laboratory reports must be reviewed by the clinical team and data entry staff, who will ensure that they are accurate and complete. Adverse events must be graded, assessed for severity and causality, and reviewed by the site principal investigator (PI) or designee.

Data collection is the responsibility of the clinical trial staff at the site under the supervision of the site PI. During the study, the investigator must maintain complete and accurate documentation for the study.

DF Net Research Inc. will serve as the Statistical and Data Coordinating Center for this study and will be responsible for data management, quality review, analysis, and reporting of the study data.

# 15.2 Data Capture Methods

Clinical data (including, but not limited to, AE/SAEs, concomitant medications, and reactogenicity data) and clinical laboratory data will be entered into a 21 CFR Part 11-compliant Internet Data Entry System, provided by DF Net Research Inc. The data system includes password protection and internal quality checks, such as automatic range checks, to identify data that appear inconsistent, incomplete, or inaccurate.

Clinical data will be entered directly from the source documents.

# 15.3 Types of Data

Data for this study will include clinical, efficacy, safety, laboratory and outcome measures.

### 15.4 Timing/Reports

A final report will be prepared following the availability of all the safety and laboratory data. Interim statistical reports may be generated as deemed necessary and appropriate by the sponsor. Safety and laboratory data summary reports may be generated for the DSMB.

### 15.5 Study Records Retention

Study documents should be retained for a minimum of 2 years after the last approval of a marketing application in an ICH region and until there are no pending or contemplated marketing applications in an ICH region or at least 2 years have elapsed since the formal discontinuation of clinical development of the investigational product. These documents should be retained for a longer period, however, if required by local regulations. No records will be destroyed without the written consent of the sponsor, if applicable. It is the responsibility of the sponsor to inform the investigator when these documents no longer need to be retained.

#### 15.6 Protocol Deviations

A protocol deviation is any noncompliance with the clinical trial protocol, Good Clinical Practice (GCP), or MOP requirements. The noncompliance may be either on the part of the participant, the investigator, or the study site staff. As a result of deviations, corrective actions are to be developed by the site and implemented promptly.

These practices are consistent with ICH E6:

- 4.5 Compliance with Protocol, sections 4.5.1, 4.5.2, and 4.5.3
- 5.1 Quality Assurance and Quality Control, section 5.1.1
- 5.20 Noncompliance, sections 5.20.1, and 5.20.2.1

It is the responsibility of the site to use continuous vigilance to identify and report deviations within 5 working days of identification of the protocol deviation, or within 5 working days of the scheduled protocol-required activity. All deviations must be promptly reported to the sponsor.

All deviations from the protocol must be addressed in study subject data collection forms. A completed copy of the Protocol Deviation Form must be maintained in the regulatory file, as well as in the participant's source document. Protocol deviations must be sent to the local IRB/IEC per their guidelines. The site PI/study staff is responsible for knowing and adhering to their IRB/IEC requirements

# **16.0 PUBLICATION POLICY**

Following completion of the study, the Investigator is expected to publish the results of this research in a scientific journal. Publication of the results of this study will be governed by sponsor policies and the International Committee of Medical Journal Editors (ICMJE) member journals, which have adopted a trials-registration policy as a condition for publication.

This policy requires that all clinical trials be registered in a public trials registry such as ClinicalTrials.gov which is sponsored by the National Library of Medicine as well as the South African National Clinical Trials Registry. Other biomedical journals are considering adopting similar policies. It is the responsibility of the sponsor to register this trial in an acceptable registry. Any clinical trial starting enrolment after 01 July 2005 must be registered on or before patient enrolment. For trials that began enrolment prior to this date, the ICMJE member journals will require registration by 13 September 2005, before considering the results of the trial for publication.

The ICMJE defines a clinical trial as any research project that prospectively assigns human participants to intervention or comparison groups to study the cause-and-effect relationship between a medical intervention and a health outcome. Studies designed for other purposes, such as to study pharmacokinetics or major toxicity (e.g., Phase 1 trials), would be exempt from this policy.

Any presentation, abstract, or manuscript will be made available by the Investigator to the sponsor, and Osel Inc. for review prior to submission.

# 17.0 SPONSOR INDEMNIFICATION FOR SITES AND INVESTIGATORS

In consideration of the sites, the Aurum Institute - Pharmacy and Females Rising Through Education, Support and Health, participation in the study, we shall indemnify and hold harmless the Aurum Institute Pharmacy and Females Rising Through Education, Support and Health and its employees from any legal liability for costs or damages for death or personal injury which may result from the administration of LACTIN-V (*Lactobacillus crispatus CTV-05*) pursuant to the said study. This indemnity does not apply to the extent that such death or personal injury arises out of any negligent act, default or omission of the Aurum Pharmacy and Females Rising Through Education, Support and Health participation in the study, we shall indemnify and hold harmless the Aurum Institute or its employees. Furthermore, this indemnity is subject to the condition that the study is carried out in accordance with the Protocol approved by us in writing, that University of California, San Francisco (UCSF) is notified immediately on receipt of any claim, that University of California, San Francisco (UCSF shall have full control of the management and defence of any such claim and that no offer to compromise or settle any claim is made without the written agreement of University of California, San Francisco (UCSF).

## **19.0 APPENDICES**

Appendix A	Schedule of Events
Appendix B	Division of AIDS Table for Grading the Severity of Adult and Pediatric Adverse Events, December 2004; Addendum 1: Female Genital Grading Table for Use in Microbicide Studies, November 2007
Appendix C	DAIDS Toxicity Table for Grading the Severity of Adult and Pediatric Adverse Events, Version 2.1 – July 2017
Appendix D	Coordination between FRESH and LACTIN-V studies

# Appendix A Schedule of Events

			Study Treatm		Study Follow-	Up				
Evaluation		Enrolment Visit 1 Day 1	Randomization Visit 3 (Day 8)	Check-In and Dosing Visits 4 - 10	Follow-Up Visit 11 Day 36	Check-In Visits 12 - 18	Final Study Visit 19 Day 64	Unscheduled Visit	Study Product Discontinuation	Early Termination Visit
Visit windov	w (Study Days)				33- 43		57-71			
Signed con	Signed consent form									
Assessment of eligibility criteria		X X	Х							
Demograph	Demographics									
Randomiza	tion		Х							
Detailed me	edical, gynaecological and sexual history	Х								
Dispense M	letronidazole	Х			(X)		(X)			
Dispense L	ACTIN-V/placebo and applicators		Х	Х						
Dispense c	ondoms	Х	Х	Х	Х	Х		Х	Х	
	al, gynaecological and sexual history		Х		Х		X	Х	Х	Х
	concomitant medications	Х	Х		Х		X	Х	Х	Х
Study interv			Х	Х						
5	Complete	X								
् ल में Symptom-directed			Х		Х		X	Х	X	Х
Symptom-directed Vital signs Pelvic examination		X	Х		Х		X	Х	X	Х
Pelvic examination			Х		Х		X	Х	Х	Х
Review syn	nptoms, AEs, menses, sexual activity			Х	Х	Х	X	Х	Х	Х
Counsel to	abstain from sexual intercourse		Х	Х	Х	Х		Х		

			Study Treatm	nent	Study Follow-	Up				
	Evaluation	Enrolment Visit 1 Day 1	Randomization Visit 3 (Day 8)	Check-In and Dosing Visits 4 - 10	Follow-Up Visit 11 Day 36	Check-In Visits 12 - 18	Final Study Visit 19 Day 64	Unscheduled Visit	Study Product Discontinuation	Early Termination Visit
	not to use vaginal products		Х	Х	Х	X		Х		
Assessmei	Assessment of adverse events			Х	Х	Х		Х	-	Х
	Clean catch urine dipstick	Х	Х		Х		Х	Х	Х	Х
	Urinalysis	(X)	(X)		(X)		(X)	(X)	(X)	(X)
-	Rapid urine βhCG pregnancy test	Х	Х		Х		Х	Х	Х	Х
Clinical Labor	Vaginal swab for N. gonorrhoeae, C. trachomatis, T. vaginalis and M. genitalium		(X)		(X)		(X)	(X)	(X)	(X)
	Vaginal swab for pH		Х		Х		Х	х	Х	Х
	PSA test for sperm exposure as POCT		Х		Х		X	Х	Х	Х
	Vaginal swab for Gram stain		Х		Х		Х	Х	Х	Х
arch atory	Vaginal swab for cytokines, HIV Target cells, vaginal bacteria, lactobacilli species		х		Х		х	х	x	х
Research Laboratory	Vaginal swab for qPCR ( L. crispatus identification)		х		х		x	х	x	х
	Cervicovaginal Lavage		Х		Х		Х	х	х	х
	Future Use vaginal swabs		Х		Х		Х	х	х	х
	Acceptability questionnaire	Х			Х				Х	Х

(X) if indicated

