#### 3.4 Study Outcome Measures

#### 3.4.1 Primary/ Secondary Outcome Measures

# *Primary / Secondary Outcome Measures for Objective 1 (effect on genital tract proinflammatory cytokines and HIV target cells)*

The proportion of participants with decreased genital tract proinflammatory cytokines and HIV target cells at 6 and 10 weeks of follow up, compared to levels at the baseline FRESH Study Visit, and Randomization Visit on Day 8 of the study (after treatment with Metronidazole is completed).

Our outcome will be a change after 4 weeks of treatment with LACTIN-V in comparison to

placebo, for the following:

- i. a decrease of the concentrations of proinflammatory cytokines in genital fluid that have been associated with risk for HIV acquisition,
- ii. a decrease in the number of activated HIV target cells (i.e. CD4+/CCR5+/HLA-DR+/CD38+ T cells) in the endocervix and
- iii. an increase the anti-HIV effect of vaginal secretions relative to placebo.

*Primary / Secondary Efficacy Outcome Measures for Objective 2 (promoting Lactobacillusdominant microbiota)* 

1:

The proportion of participants with increased *Lactobacillus*-dominant vaginal microbiota in young South African women, compared to levels at randomization (Day 8) after completion of metronidazole. Measured will be overall *Lactobacillus* species, as well as *Lactobacillus crispatus*, *Lactobacillus jensenii*, *Lactobacillus gasseri*, and *Lactobacillus iners*.

Our primary outcome is the presence of *Lactobacillus*-dominant vaginal microbial cervicotypes after 4 weeks of treatment with LACTIN-V, and following the post- dosing phase at Day 64.

Secondary outcomes include comparison of *L. crispatus* vs. *L. iners* prevalence between treatment groups, persistence of colonization after stopping therapy, effect of sex and/or vaginal hygiene practices on colonization by lactobacilli, and stability of vaginal microbial communities over time in the treatment vs. placebo group.

2:

The proportion of participants with a positive BV diagnosis in each study arm by Day 64.

BV is defined Nugent score 7-10. Following FDA guidance all BV diagnoses during follow-up visits are considered incident, as they occur at least 22-30 days after the commencement of Metronidazole treatment and consequently are treatment failures or new infections. For the purpose of this trial, treatment failure and new infection will both be considered recurrent BV.

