At the **Enrolment Visit 1 (Day 1)**, participants will complete a medical history and undergo a physical examination. Enrolled participants will receive oral Metronidazole 400mg tablets, and are instructed to immediately start the 7-day course (twice daily), to be completed within 8-48 hours of the Randomization Visit on Day 8. A **Check-In Visit 2 (Day 4)** is scheduled to provide additional guidance for the metronidazole administration.

At the **Randomization Visit 3 (Day 8)**, a gynaecological exam will be conducted to collect baseline vaginal microbiome data, including cervical swabs, cervicovaginal lavage fluid and an endocervical cytobrush to assess the microbial composition, cytokines and mucosal HIV target cells. A gram stain and a vaginal swab for *L. crispatus* (including CTV-05) identification will be collected. Only participants who completed their 7-day course of oral Metronidazole will be randomized and receive study product.

The 11 doses of LACTIN-V at 2 x 10^9 cfu/dose or placebo are scheduled to be administered by vaginal applicator for 5 consecutive days and then twice weekly for 3 weeks, throughout Week 1-4 of the study. The first dose of study product is administered as part of the Randomization Visit on Day 8. Participants will be instructed to take the second and third dose on subsequent Days 9 and 10 at home before bedtime. All other doses will remain at the clinic site, where the women are attending regular twice-weekly visits as participants of the FRESH study. During these FRESH visits, they will be handed the remaining LACTIN-V applicators to administer on site according to schedule in a form of directly observed therapy.

During the study, participants will be counselled to use the provided lubricated or unlubricated nonspermicidal condoms during vaginal intercourse. Study staff will provide condoms that have been tested to not interfere with lactobacilli growth. In addition, participants are counselled to avoid vaginal intercourse during the 12 hours before scheduled gynaecological exams, as this activity could lead to microabrasions notable at speculum exam, and could interfere with a correct determination of symptoms related to study product administration. Further, participants will be counselled to avoid sexual intercourse for 12 hours after study product administration to ensure that the product will remain inside the vagina.

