**Brief Check-in Follow-up Visits 4 - 10 (Days 11, 15, 18, 22, 25, 29 and 32)** without physical and gynaecological exams to assess adherence, menstrual cycle, sexual activity, condom use, concomitant medications, and AEs, and to administer subsequent doses of study product are scheduled to coincide with regular clinic visits as part of the FRESH schedule (twice weekly either Monday/Thursday or Tuesday/Friday).

Week 1:	Day 8 (where the doses for Day 9 & 10 are handed to participants to take at
	home)
	Day 11 (where the dose for Day 12 is handed to participants to take at home)
Week 2:	Day 15 and 18 (Doses 6 and 7) administered in clinic
Week 3:	Day 22 and 25. (Doses 8 and 9) administered in clinic
Week 4:	Day 29 and 32. (Doses 10 and 11) administered in clinic

At the beginning of Week 5, at the end of the dosing phase, a **Follow-up Visit 11** is scheduled for **Day 36**. This visit will include a physical and gynaecological exam to collect vaginal microbiome data, including cervical swabs, cervicovaginal lavage fluid and an endocervical cytobrush to assess the microbial composition, cytokines and mucosal HIV target cells. A gram stain and a vaginal swab for L. crispatus (including CTV-05) identification will be collected.

Should symptoms or the sexual history suggest the acquisition of an STI, testing for STIs will be included. Acceptability will be assessed using a questionnaire.

During Week 5 – 8, study staff will continue to check in with participants twice weekly for brief **Checkin Follow-up Visits 12 – 18 (Days 39, 43, 46, 50, 53, 57 and 60)** without physical and gynaecological exams to assess menstrual cycle, sexual activity, condom use, concomitant medications, and AEs. These are scheduled to coincide with regular clinic visits as part of the FRESH schedule (twice weekly either Monday/Thursday or Tuesday/Friday).

Week 5:	Day 39
Week 6:	Day 43 and 46
Week 7:	Day 50 and 53
Week 8:	Day 57 and 60

The **Final Visit 19 (Day 64)** 4 weeks post dosing will include a physical and gynaecological exam to collect vaginal microbiome data, including cervical swabs, cervicovaginal lavage fluid and an endocervical cytobrush to assess the microbial composition, cytokines and mucosal HIV target cells. A gram stain and a vaginal swab for L. crispatus (including CTV-05) identification will be collected. Should symptoms or the sexual history suggest the acquisition of an STI, testing for STIs will be included.

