# 7.3 Randomization Visit 3 (Day 8)

Before commencing with the physical and gynaecological exam, eligibility for randomization should be confirmed by reviewing the medical history and all laboratory results.

Only women who had negative STI tests and a Nugent score 4-10 on the vaginal specimen collected at the Week 5 FRESH Study Visit, are enrolled in LACTIN-V and completed a full 7-day course of oral Metronidazole (at least 12 of 14 doses, last dose within 8-48 hours of Randomization Visit 3) will proceed to be randomized. Women who did not complete a full 7-day course of oral Metronidazole and took less than 12 of 14 doses, or took the last dose more than 48 hours before the Randomization Visit 3, will be withdrawn from the study.

Participants will be asked to verify previously reported contact information which will be recorded on the appropriate form.

Additionally, her menstrual cycle history will be re-evaluated to ensure regular menstrual cycles (or amenorrhea with long-acting contraceptives) and that menstruation will not be expected during the next 5 days when the use of the study product for 5 consecutive days (days 1-5) has to occur. If she is not currently having menstrual bleeding and her period is not to be expected within the next 5 days, she will proceed with the Randomization Visit 3.

Participants will undergo the following procedures at the Randomization Visit 3 (Day 8):

- 1. Review of concomitant medications
- 2. The pelvic examination will be conducted in the following order:
  - a. Examination of the external genitalia
  - b. Speculum insertion and examination of vagina, fornices and cervix with naked eye. Water will be used to ease speculum insertion. No lubricant should be used as it could contain chlorhexidine which may kill *Lactobacillus*.
  - c. Vaginal pH
  - d. Vaginal swab for Gram stain (Nugent scoring system)
  - e. Two Vaginal swabs for complete mucosal sampling including identification of vaginal bacteria, lactobacilli species, cytokines and HIV target cells as well as multiomic (e.g. proteomics, metabolomics, etc.) testing
  - f. Cervical (or vaginal) swabs for nucleic acid amplification of N. gonorrhoeae, and C. trachomatis.

- g. A cervicovaginal lavage sample
  h. Vaginal swabs for *L. crispatus* identification with qPCR
  i. Vaginal swab for prostate specific antigen testing as a proxy for recent exposure to semen

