## 8.2 Laboratory Evaluations

8.2.1 Clinical Laboratory Evaluations

At the clinical site, the following tests will be performed using approved standard inhouse tests:

- Pregnancy will be tested by standard rapid urine βhCG assays.
- Urine will be tested by urine dipstick for evidence of urinary tract infection, with follow-up urinalysis (UA), if abnormal.
- HIV testing will be conducted using standardized algorithms.\*
- Cervical (or vaginal) swabs will be tested for *N. gonorrhoeae*, *T. vaginalis*, *Mycoplasma genitalium* and *C. trachomatis* by nucleic acid amplification.
- Gram-stained vaginal smear by Nugent's scoring system for diagnosis of BV
- 8.2.2 Special Assays or Procedures
  - Vaginal specimens will be analyzed for vaginal colonization with *L. crispatus* using qPCR assays and 16S rRNA gene/shotgun sequencing, which will be performed by a central laboratory at the Ragon Institute of MGH, MIT and Harvard
  - Cervicovaginal lavage (CVL) specimens will be analyzed for cytokines and chemokines using a luminex array
  - Cervical cytobrush samples will be used to assess presence of HIV target cells by flow cytometry.
  - Vaginal specimens will be analyzed using multiomic (e.g. proteomics, metabolomics, etc.) testing.
  - Vaginal samples will be used for culturing of live bacterial isolates for quenching and functional analysis
  - CVL will also be used for in vitro anti-HIV activity assays

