# 11.3 Sample Size Considerations

The study will accrue a total of 60 randomized subjects (n=20 for the placebo arm A and n=40 for the LACTIN-V arm B). The accrual for this study is expected to be completed within 75 weeks (18 months) with projected accrual rate of 3 subjects per month. Each subject will be followed up for 64 days.

The primary endpoint upon which the sample size calculation was based is the proportion of subjects with a  $\geq 1 \text{ Log}_{10}$  decrease in at least 3 of 9 proinflammatory cytokines in CVL specimens on the Day 36 Visit, i.e. at the completion of the LACTIN-V/Placebo dosing phase. The proportion of women with decreased inflammation will be compared between the two study arms. This endpoint is adapted from the CAPRISA 004 study which demonstrated that women with the highest levels of at least 3 of 9 proinflammatory cytokines in CVL specimens had an increased risk of HIV acquisition. Our adaptation of the CAPRISA 004 analysis is that we will define "decreased inflammation" as a  $\geq 1 \text{ Log}_{10}$ decrease in the concentration of at least 3 of the same 9 proinflammatory cytokines. Based on our prior data, we assume that no more than 10% of placebo-treated women will achieve a decrease in  $\geq 3$  of the 9 proinflammatory genital tract cytokines. Moreover, we hypothesize that at least half of the participants in the treatment arm will achieve a decrease  $\geq 1 \log_{10}$  in  $\geq 3$  of the 9 proinflammatory genital tract cytokines. With the targeted sample size of 60 randomized women (1/3 in placebo arm & 2/3 in the LACTIN-V arm; there will be more than 88% power to detect a 40% absolute difference (10% vs. 50%) in the proportion of women with decreased inflammation between the two treatment arms. This power calculation was based on simulation study using 10,000 Monte Carlo samples and two-sided Fisher's exact test with type 1 error rate of 5%.

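### The Section 7 exam lists and Appendix A omit the endocervical cytobrush that Sections 4.0 and 8.2.2 require, and assign HIV target cells to vaginal swabs

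*Combined protocol and SAP*

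**What the plan says.** Section 3.4.1 lists among the Objective 1 outcomes "a decrease in the number of activated HIV target cells", and locates those cells in the endocervix. Section 11.2 repeats the outcome as endocervical CD4+ target cells at Days 36 and 64 compared with baseline, and Section 11.5 places target cells within the primary analyses for Objective 1.

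Section 4.0 describes the gynaecological exams at Days 8, 36 and 64 as collecting material "including cervical swabs, cervicovaginal lavage fluid and an endocervical cytobrush to assess the microbial composition, cytokines and mucosal HIV target cells". Section 8.2.2 ties each analyte to a specimen. For target cells, "Cervical cytobrush samples will be used to assess presence of HIV target cells by flow cytometry". For lavage, "specimens will be analyzed for cytokines and chemokines using a luminex array". Section 11.3 defines the endpoint used for sample size on "proinflammatory cytokines in CVL specimens on the Day 36 Visit".

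The operational text differs. The pelvic-exam lists in 7.3, 7.5, 7.7, 7.8 and 7.9 are presented as the sequence in which the exam is done. Each contains the line "Two Vaginal swabs for complete mucosal sampling including identification of vaginal bacteria, lactobacilli species, cytokines and HIV target cells", and none contains a cytobrush. The matching research-laboratory row in Appendix A is "Vaginal swab for cytokines, HIV Target cells, vaginal bacteria, lactobacilli species", and the grid has no cytobrush row.

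**The concern.** The visit lists and the schedule are the parts of a protocol that lay out collection step by step. Here they do more than leave the cytobrush out: they name another specimen for the same measurement. A clinician who completed every lettered item could reasonably believe the target-cell sample had been taken.

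A vaginal swab does not sample the endocervix, so it does not supply the outcome as Section 3.4.1 defines it. A cytobrush missed at Day 8 loses the post-metronidazole comparison for that woman. One missed at Day 36 or Day 64 loses the on-treatment or post-dosing value. None can be collected later.

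**Working it through.** The plan gives no figure on this point, so the check is a comparison of its specimen lists.

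| Place | Visit | Cytobrush named? | Specimen given for HIV target cells | CVL named? |
|---|---|---|---|---|
| 4.0 | Days 8, 36, 64 | Yes, all three | Cervical swabs, CVL and cytobrush as a set | Yes |
| 8.2.2 | Assay section | Yes | Cervical cytobrush, flow cytometry | Yes, for cytokines |
| 8.2.3 | Handling and storage | Yes (cytobrush cells) | Not stated | No |
| 7.3 | Visit 3, Day 8 | No (items a to i) | Two vaginal swabs | Yes |
| 7.5 | Visit 11, Day 36 | No (items a to i) | Two vaginal swabs | Yes |
| 7.7 | Visit 19, Day 64 | No (items a to j) | Two vaginal swabs | Yes |
| 7.8 | Discontinuation or early termination | No (items a to j) | Two vaginal swabs | Yes |
| 7.9 | Unscheduled | No (items a to j) | Two vaginal swabs | Yes |
| Appendix A | Grid | No row | Vaginal swab | Yes, own row |

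**Count.** The cytobrush appears at 3 of 3 gynaecological visits in Section 4.0, in 0 of 5 exam lists in Section 7, and in 0 rows of Appendix A. The lettering in each list runs without a gap, and the five lists and the grid agree with one another, so this is not a line lost in reading the PDF.

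**Most that could be affected.** Specimens per woman = scheduled gynaecological visits = 3. Across the trial, 3 × 60 = 180 (3 × 40 = 120 on LACTIN-V and 3 × 20 = 60 on placebo). This is the ceiling if every collector followed the Section 7 lists alone. It is not a forecast.

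**Could FRESH sampling fill the gap?** Section 2.5 says FRESH collects cytobrushes every three months. Taking three months as about 90 days, compare the span of the trial visits: 64 − 8 = 56 days, or 71 − 8 = 63 days at the late edge of the final-visit window. Both are shorter than 90 days. At most one FRESH cytobrush could therefore fall within the span, and nothing aligns it with Day 8, 36 or 64.

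**Cytokines.** Every exam list and the grid carry CVL as its own item. The specimen that 8.2.2 and 11.3 name for cytokines is therefore collected whichever section staff follow. Naming cytokines on the vaginal-swab line is a labelling fault. It leaves two candidate specimens on paper but removes neither.

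**The case against.** The best case against the point is that the protocol is not silent. Section 4.0 names the cytobrush at all three visits, 8.2.2 gives its assay, 8.2.3 says where the cells are processed, and 5.3.4 presupposes cervical samples by exempting pregnant women from them. There is one site, the FRESH clinic, where cytobrushes are routine; Section 2.5 reports more than 6,000 stored CVL and cytobrush samples. The swab line in Section 7 refers to full mucosal sampling, which in FRESH includes the cytobrush. Specimen instructions are deferred to the MOP, which is not available, and Appendix D on coordination with FRESH survives only as a heading. Either may list the cytobrush.

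Most of this stands as to likelihood. A reader might infer that the specimen will not be collected and the target-cell outcome will be lost. The documents do not support that: the requirement is explicit in Section 4.0, and nothing shows that staff will follow Section 7 in preference to it. A reader might also infer a threat to the primary cytokine endpoint. That fails because CVL is in every list.

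What the objection does not remove is the contradiction. Site experience and an unseen manual do not change a line that names two vaginal swabs. A visit run strictly to the list departs from Section 4.0, while a visit run to Section 4.0 includes a step with no place in the prescribed order. Section 15.6 treats any noncompliance with the protocol as a deviation, so a missing cytobrush could not be classified cleanly.

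**Conclusion.** The point holds as an internal inconsistency that should be corrected. The design is clear in Sections 4.0 and 8.2.2; the operational text in 7.3, 7.5, 7.7 and Appendix A does not match it, for an outcome that Section 11.5 counts among the primary Objective 1 analyses.

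The exposure is at most 3 irrecoverable specimens per woman. How many would actually be missed cannot be estimated from the documents; it depends on the MOP, the case report forms and site practice. The endpoint behind the sample size is unaffected.

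A reader might also conclude that a cytobrush belongs in 7.8 and 7.9. The documents do not support that as it stands. Section 4.0 asks for it only at Days 8, 36 and 64. Section 7.8 also covers women who stop product because of pregnancy (listed in 5.3.3.1), for whom 5.3.4 excludes samples taken directly at the cervix. An unqualified line there would create a new contradiction.

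**What to change.** 1. Add an endocervical cytobrush line for HIV target cells, at a stated place in the exam order, to 7.3, 7.5 and 7.7. Add a matching row to Appendix A at Visits 3, 11 and 19. Cross-refer both to the pregnancy exception in 5.3.4.
2. Remove HIV target cells from the vaginal-swab lines in 7.3, 7.5, 7.7, 7.8 and 7.9 and from the swab row in Appendix A.
3. Have the sponsor state whether a cytobrush is intended at the 7.8 and 7.9 visits, and word those sections and the grid to agree.
4. As a labelling correction only, state that cytokines for the primary endpoint are measured in CVL, consistent with 8.2.2 and 11.3.
5. Check the MOP and the case report forms against the corrected lists.

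The cost is protocol wording, one schedule row and the matching case report form entry. No procedure is added at Visits 3, 11 and 19, because Section 4.0 already requires the cytobrush there. A cytobrush at the 7.8 or 7.9 visits would be new, which is why step 3 asks for a decision.
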